
4) Chart review: VA health services utilization will be obtained from VA chart review for all consenting participants. Utilization measures will include: enrollment in VA, MHV enrollment, secure messaging of results, initiation of telephone or face-to-face contact with a provider or TPA interface about screens or secure messaged results, and MH consult sent or services receipt and location (in PC, PCMHI, or MH). We developed an efficient electronic and chart reviewer interface in our CREATE study, which will be leveraged for this study. The VA EMR will be electronically checked monthly for up to 6 months following WEB-ED completion. Chart reviews will encompass VA purchased care records (inclusive of non-VA provider care received via Choice).

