In summary, phase 1 involves qualitative interviews with key stakeholders/informants; phase 2 involves online intervention (Web-Ed) and RCT; phase 3 involves process evaluation post-intervention, which will involve data collected via Computer-Assisted Telephone Interview (CATI) to determine intervention effectiveness via semi-structured telephone interviews. Chart review will be performed 6 months post phase 2 web intervention. For the WEB-ED in phase 2, if the subject is eligible per the pre-consent screening questions, the informed consent for this online process is integrated into the web-based subject education and participants acknowledge (“click approval”) that they have reviewed this prior to participation (attachment 2A Consent Letter - Current Web-Ed). This online document containing the elements of consent will contain the same information as the mailed document and will also inform participants that they may be invited to participate in a subsequent study phase that will address VA and post-deployment care access.

Veteran participants will provide consent for RCT portion of phase 2 (as assigned), the phase 3 telephone interview, and chart review by signing and returning via mail the consent and HIPAA forms prior to participating in the RCT portion of phase 2. For those who participate in the first part of phase 2 and are eligible for the RCT portion of the study, they will be asked online at WEB-ED completion for permission to re-contact them about continuing their participation in the RCT (Web-Ed+). Those who indicate yes will be sent IRB approved study information, including the RCT consent letter (2B), consent and HIPAA forms attached to this application. Those who decline will be thanked again for their participation and contact will be discontinued.

I.5 **Specify your research question(s), study aims or hypotheses (do not indicate "see protocol")**

Specific Aim #1: To obtain key stakeholder perspectives regarding refinement of WEB-ED, including enhancement with shared-decision making (SDM) interventions, linkage with MyHealtheVet (MHV), and VA enrollment materials.

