Phase 2 WEB-ED Recruitment: participants selected from the VA Informatics and Computing Infrastructure (VINCI)/VA/DoD Identity Repository (VADIR) and per Defense Manpower Data Center (DMDC) will be recruited with a mailed recruitment letter (attachment 2A) containing the elements of consent, e-mail, and telephone follow up using call protocols. If we have not heard from the subject within 10 days of the initial mailing, a follow-up email (2C for Web-Ed and 2D for RCT) will be sent with “Do Not Reply” added to the subject line. If we have not had participant contact by 10 days after sending the email, we will resend an additional email. If there is still no response, we will initiate telephone contact consisting of 3 total calls during different times of the day (morning, afternoon, evening) in attempts to address any questions and to encourage online screening completion. A toll-free number will be provided to participants to facilitate contact for any questions. Bad Contact Info Call Script and Email will be used to contact subjects in effort to update their contact information. For the WEB-ED, if the subject is eligible per the pre-consent screening questions, the informed consent for this online process is integrated into the web-based subject education and participants acknowledge (“click approval”) that they have reviewed this prior to participation (attachment 2A Consent Letter - Current Web-Ed). This online document containing the elements of consent will contain the same information as the mailed document and will also inform participants that they may be invited to participate in a subsequent study phase that will address VA and post-deployment care access.

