Veteran participants will provide consent for RCT portion of phase 2 (as assigned), the phase 3 telephone interview, and chart review by signing and returning via mail the consent and HIPAA forms prior to participating in the RCT portion of phase 2. For those who participate in the first part of phase 2 and are eligible for the RCT portion of the study, they will be asked online at WEB-ED completion for permission to re-contact them about continuing their participation in the RCT (Web-Ed+). Those who indicate yes will be sent IRB approved study information, including the RCT consent letter (2B), consent and HIPAA forms attached to this application. Those who decline will be thanked again for their participation and contact will be discontinued.

VII.D.37 *Does the study include any form of deception (e.g., providing participants with false information, misleading information, or withholding information about certain study procedures)?*

Examples:

- *Procedure includes a cover story that provides a plausible but inaccurate account of the purposes of the research.*
- *Participants will be provided with false information regarding the particular behaviors of interest in the research.*
- *Procedures include a confederate pretending to be another participant in the study.*
- *Participants will be told that the research includes completion of a particular task, when in fact, that task will not be administered.*
- *Study is designed to introduce a new procedure (or task) that participants are not initially told about.*
- *If yes, a waiver of informed consent must be requested under question IV.3.*

No

VII.E. Project Description (E)

VII.E.1 *Will subjects be randomized?*
Yes

VII.E.1.a *Will any subjects be blinded to which study arm they have been assigned?*
No

VII.E.2 *Describe randomization scheme/assignment including ratio such as 1:1, 2:1 etc.*

For phase 2, we will use adaptive randomization to assign positive-screenerers to each RCT arm; two-thirds to WEB-ED+ (~950) and one-third to Current WEB-ED (~450).

VII.E.3 *Will any questionnaires, surveys, or written assessments be used to obtain data directly from subjects in this study?*
Yes

VII.E.4 *List all questionnaires, surveys, written assessments and ATTACH each one to the application. (NOTE: You are NOT prohibited from attaching copyrighted materials to this application)*

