Phase 2 RCT Intervention (WEB-ED+) Provider Procedures: once the provider has agreed to participate, they will be sent an email that contains links to 2 short videos about shared decision-making and three brief decision aids (PTSD, depression, substance use disorder).

Using the knowledge both the provider and patient learned from the WEB-ED+ materials, they will discuss treatment options at the patient's appointment.

If subjects do not complete steps in the process, the appropriate attachment (Phase 2 RCT missing VA enrollment, Phase 2 RCT missing MHV premium enrollment, or Phase 2 RCT missing secure messaging) will be sent via email or postal mail if email is not available to support completion of these steps, with a toll free number provided. Further, up to 3 contact calls will be made until the subject is reached, to determine if the participant has discontinued study participation, if the study team can be of further assistance, or to determine the completion barrier(s), and if the Veteran is enrolled- to assist them with MHV barriers by sending the study screening results summary by encrypted email to the participant's preferred or new provider in their stead (eSDM Chart Review-Secure Message) so they are able to progress to their appointment in order to use shared decision-making with their provider about their positive MH screens. Requested Resources Email Scripts will be sent per request of subject as needed. The missing email notice attachment will be used for those in the treatment arm of RCT to encourage them to contact us and update their email address so we can continue their participation with the study. The provider consent notification document will be sent via mail or email letting the participant know that their provider has consented to participate in the RCT.

Those who decline will be thanked again for their participation and contact will be discontinued. We will use adaptive randomization to achieve balance in the assignment of those who consent to WEB-ED+ or Current WEB-ED. Those who are assigned to Current WEB-ED will not be contacted again until Phase 3.

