Per VA Research project modification approval received November 2022, we are now able to provide subjects with an additional \$30 for already returned signed HIPAA form and consent to participate with this study phase. We will notify previous subjects using attachments (Phase 2 New Reimbursement postal mail and Phase 2 New Reimbursement email), and submit this request, anticipating that they should receive this direct deposit within 4 to 8 weeks. For new RCT recruitments we have edited the Phase 2 RCT recruitment to indicate that if they return their signed HIPAA form and consent to participate in this study phase they will receive \$50.00 (the same amount as those who have already returned these forms will receive).

Because of new VA research policy changes, we are now also able to provide subjects with an additional \$75.00 upon completion of the RCT "intervention group" steps of this research phase that involves seeing their VA provider (as described in the consent and the

encrypted study group assignment email).

We will send the new funding notice to all RCT consenters first by email, followed by postal mail with follow up a week later via telephone using a 3-call protocol.

If subjects do not complete the screening, attachments Phase 2G Incomplete Survey Email and Phase 2H Incomplete Survey Letter will be sent to encourage completion.

A medical chart review will be conducted for the subjects who return the signed HIPAA and consent forms for the RCT and prior to the interview for phase 3. Chart reviews will focus on VA outpatient care the subject received (or not) including medication, therapy, & substance use treatment. We will review the time from post-deployment through 6 months after the subject's initial study participation. We will assess/confirm enrollment status and upcoming appointments of participating Veterans using a combination of national visual chart review using CAPRI/JLV, along with accessing enrollment and appointment data from the CDW.

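### The 6-month chart window for the primary outcome runs from WEB-ED rather than from assignment, and the visible text states neither an explicit outcome start date nor a settled moment of assignment

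*Combined protocol and SAP*

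**What the plan says.** Three formulations set the end or timing of chart follow-up, and none refers to assignment.

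- Research plan, section 4.0, chart review item: "The VA EMR will be electronically checked monthly for up to 6 months following WEB-ED completion". The same item says that "VA health services utilization will be obtained from VA chart review for all consenting participants".
- IRB application, I.4: "Chart review will be performed 6 months post phase 2 web intervention".
- IRB application, VII.D.29 and VII.E.6: "We will review the time from post-deployment through 6 months after the subject's initial study participation".

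The Aim 2 analysis text (section 4.0 and XI.1) defines care engagement only as receipt of VA mental health services, yes or no. It gives no start date and no rule on earlier care. Section XIII.1 says that a chart review template is attached. That template is not in the text available here and may contain such a rule.

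On the timing of assignment the documents differ. Section VII.D.29 says that Veterans consent to the RCT "by signing and returning via mail the consent and HIPAA forms prior to participating in the RCT portion of phase 2", and VII.E.6 states: "We will use adaptive randomization to achieve balance in the assignment of those who consent to WEB-ED+ or Current WEB-ED". The recruitment paragraph of section 4.0 agrees. The sample-size text (section 4.0 and XI.2) and VII.E.2 instead describe assigning those who screen positive.

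**The concern.** Care received before assignment cannot be an effect of WEB-ED+. If assignment waits for forms returned by mail, the stated window opens before the randomised comparison does. Visits in that gap count toward engagement in both arms and dilute the contrast. The period in which WEB-ED+ can act is 6 months minus the gap, so 6-month engagement covers a shorter post-assignment period for a Veteran who consents late than for one who consents early.

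Prior care bears on this too. Earlier VA mental health use is collected in the pre-intervention survey and the chart review (VII.E.6) but is not among the covariates named in XI.1. That list is open-ended, so this is a gap to close rather than an error.

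**Working it through.** **Inputs from the plan.** Control engagement of 25% to 35%; OR 1.5, 1.8 and 2.0; about 450 Veterans on Current WEB-ED; about 950 assigned to WEB-ED+, of whom 650 are expected to complete (section 4.0, Aim 2 Sample Size and Power).

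**Assumptions.** The WEB-ED-to-assignment lag is not in the documents; 10, 20 and 60 days are pure assumptions. Six months is taken as 182 days, with a constant hazard in the control arm. Alpha is not stated, so 5% is shown both two-sided and one-sided.

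**Reproducing the plan's figure.** For a 25% control rate and OR 1.5, the WEB-ED+ rate is 1.5 × 0.25 / (0.75 + 1.5 × 0.25) = 0.3333. A pooled-variance two-proportion test at one-sided 5%, 2:1 allocation and 80% power needs 278 + 556 = 834, as printed. Two-sided, the total would be 1,059. Eight of the nine cells without variance inflation reproduce at one-sided 5%.

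**Dilution model.** C is the control rate over the full window and d the lag in days.

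- Share of control engagement falling before assignment: s = (1 − 0.75^(d/182)) / 0.25, giving 0.063, 0.124 and 0.362; run at 0.06, 0.12 and 0.36.
- Engaged before assignment, same in both arms: q = s × C.
- Control rate among the rest: r = (C − q) / (1 − q).
- WEB-ED+ odds among the rest: o = OR × r / (1 − r).
- WEB-ED+ rate over the window: T = q + (1 − q) × o / (1 + o).

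Example, 20 days: q = 0.12 × 0.25 = 0.03; r = 0.22 / 0.97 = 0.2268; o = 1.5 × 0.22 / 0.75 = 0.44; T = 0.03 + 0.97 × 0.44 / 1.44 = 0.3264. The observed OR is (0.3264 / 0.6736) / (0.25 / 0.75) = 1.45.

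Results for C = 25%, OR 1.5 and 450/650, without variance inflation:

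| Assumed lag | Days left of 182 | WEB-ED+ rate | Observed OR | Power, two-sided | Power, one-sided |
|---|---|---|---|---|---|
| 0 | 182 | 33.3% | 1.50 | 85% | 91% |
| 10 days | 172 | 33.0% | 1.48 | 82% | 89% |
| 20 days | 162 | 32.6% | 1.45 | 78% | 87% |
| 60 days | 122 | 31.1% | 1.35 | 59% | 71% |

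**Sensitivity (two-sided; lags 0, 10, 20, 60 days).**

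- All 950 assigned to WEB-ED+ analysed: 89%, 87%, 84%, 65%.
- Control rate 35%, 450/650, same shares: 90%, 88%, 85%, 70%.
- Control rate 25%, 450/650, OR 1.8: at least 91% throughout. OR 2.0: at least 98%.

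**Second model.** Here the hazards are fixed so that a full 182 days would give 25% and 33.3%, and both arms have the control hazard before assignment. Two-sided power with the window as written is 81%, 77% and 54% at 10, 20 and 60 days. The 60-day figure is below the 59% in the table because the hazards, rather than OR 1.5 in the shortened window, are held constant. Counting only care from assignment to the existing end date gives 83%, 81% and 71%. These are two-proportion calculations with one common lag for all Veterans.

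**The case against.** The strongest reply is that assignment may be almost immediate. The positive-screener wording fits that. So does VII.E.6, which, under the WEB-ED+ procedures, has Veterans return the form on concerns to share with their provider together with their signed consent. On that reading the loss is near zero. This stands as a limit on the size of the problem, but it also shows that the moment of assignment is unsettled.

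A second reply is that a start date is implied: the monthly record checks in section 4.0 follow WEB-ED completion, and the unseen template may state one. This is fair, but a WEB-ED start would still let care before assignment count.

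Third, a window from WEB-ED, which both arms complete, remains a valid randomised comparison. This is correct; it is diluted, not biased toward WEB-ED+.

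A reader might infer more than the documents support in three places:

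- **The reminder schedule as a documented lag.** VII.D.29 says that "within 10 days of the initial mailing, a follow-up email (2C for Web-Ed and 2D for RCT) will be sent", and then "If we have not had participant contact by 10 days after sending the email, we will resend an additional email". That paragraph concerns WEB-ED recruitment. The next one describes the RCT email as going to those who have not finished steps set by randomisation, so it may come after assignment. The reminders do not establish a lag.
- **All care since deployment counting as the outcome.** The look-back defines what is reviewed. No section says that earlier care scores as engagement.
- **Two outcome windows, one per arm.** VII.E.6 does mention separate post-RCT and post-WEB-ED 6-month points, but only for Phase 3 interview contact.

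**Conclusion.** The point holds as a matter of definition. Every stated chart window is tied to WEB-ED or initial participation, the outcome has no explicit start in the visible text, and the timing of assignment is described in two ways. Where assignment follows mailed consent, care that assignment cannot have caused may count, and post-assignment follow-up is shorter than 6 months by a varying amount.

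The harm is dilution and lost power. A reader might infer an inflated type I error or an advantage to WEB-ED+. Neither follows, because the same window applies to both arms and care before assignment is balanced in expectation.

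The size depends on a lag that the documents do not give. At assumed lags of 10 and 20 days the loss at OR 1.5 is modest; at the one-sided level that matches the plan's table, power stays above the planned 80%. Only the assumed 60-day lag costs much, and mainly at OR 1.5. The change is worth making because it is cheap and gives the primary comparison a clear meaning.

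**What to change.** - **Outcome.** Define it as at least one VA or VA-purchased mental health service dated after the assignment date and within 6 months of it, with the same window in both arms. Use earlier chart data as baseline only.
- **Assignment.** State when it occurs relative to consent, and reconcile the positive-screener wording with the consenter wording.
- **Covariate.** Add VA mental health care before assignment, with a look-back period fixed in advance, to the primary logistic model. A separate analysis of new engagement among Veterans without such care is optional.
- **Fallback.** If the signed forms do not permit the later end date, count only care from assignment to the existing end date and account for each Veteran's days at risk. A complementary log-log model with log days at risk as offset would do this, but it reports a hazard-type effect rather than the planned odds ratio, and the plan should say so. The power figures above do not test that model.

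The cost is revised wording, re-dating of encounters from the existing chart and data-warehouse sources, and a chart look-up that runs later by the consent lag. The sponsor must confirm that the signed consent and HIPAA forms cover the later date. VII.D.29 has both arms sent an assignment letter, so an assignment date should be recoverable, although no section says that it is recorded. The definition should be fixed before outcomes are compared by arm.
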